#### Interventions and exposures.

Aims 1 & 2. To examine the effects of maternal infection with intestinal nematodes or schistosomiasis, and of the treatment of maternal nematode infection or schistosomiasis in **pregnancy.** Mothers will be randomised to receive albendazole or placebo and praziguantel or placebo during the second to third trimester of pregnancy. A marked reduction in IFN-y response after BCG immunisation has been demonstrated for children of mothers with schistosomiasis or filariasis but the effects of intestinal nematodes, and the effects of treatment of helminths in pregnancy, including both intestinal nematodes and Schistosoma sp, are not known. We will determine the effect of intestinal nematodes by comparing children of mothers with and without intestinal nematodes during pregnancy (Appendix 4). If intestinal nematodes have an effect similar to schistosomiasis or filariasis, treatment of all or any of these groups of helminths in pregnancy may be beneficial for the response to immunisation in the neonate. This will be determined for individuals known to have had helminths before treatment, and for all participants (Appendix 4). If, however, treatment leads to an increase in type 2 bias, as has been documented in studies for schistosomiasis (Appendix 1, Figure 3), suppression of the neonatal type 1 response may be increased. For the same reason, treatment in pregnancy may have benefits, or disadvantages, for the neonate's susceptibility to bacterial or viral infections. For vertical transmission of HIV infection, treatment in pregnancy may have benefits for the immune response, or may enhance vertical transmission through a transient rise in viral load (Appendix 1, Figure 1). Thus, for our objectives, a randomised trial of treatment in pregnancy is appropriate. Other considerations are as follows. Treating hookworm in pregnancy can reduce anaemia,  so women with hookworm and severe anaemia will be excluded from randomisation and treated. Treating helminths may improve the mother's general health, and hence birth outcome (stillbirths, perinatal deaths, birthweight), but this has not been demonstrated in controlled trials; and there is a possible risk of teratogenicity, but this may be confined to the first trimester. Therefore, although these outcomes are not the main issue for this study, they will be recorded and considered in an interim analysis.

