Aim 3. To examine the effects of acquisition of intestinal nematodes during childhood and of regular mass treatment in childhood. *After one year of age, children will be randomised to receive albendazole or placebo every 3 months. Both groups will receive annual, selective treatment based on stool analysis.* Prior helminth infection is associated with impaired responses to immunisation, but it is not certain whether acquisition of helminths leads to loss of an established response, or increased susceptibility to bacterial and viral infections, and whether this can be prevented by regular de-worming. This will be determined by comparing children who receive regular de-worming as well as annual, selective treatment with those who receive annual, selective treatment only (groups C1 vs C2, appendix 4). Prevention of helminth infections may have disadvantages, such as increased risk of severe malaria and thus, for our objectives, a randomised trial is appropriate. Other considerations are as follows. Regular de-worming may have benefits for growth and cognitive performance in childhood, but a recent meta-analysis has shown that the evidence, particularly relating to cognitive performance, is still inconclusive. Again, these outcomes are not the main issue for this study, but will be recorded.

**Aim 4.** To examine the effects of childhood schistosomiasis. This component will be observational because the incidence of schistosomiasis in children under 5 is not expected to be high enough to justify mass treatment. As in the case of intestinal nematodes, we wish to investigate whether acquisition of helminths leads to loss of an established response to immunisations, and influences susceptibility to other infections. For this observational component, important potential nutritional and environmental confounding factors for the effects of helminths are known to exist. These will be recorded and appropriate adjustments will be made.

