**Outcome (2): immunological responses to HIV in children of HIV-1 infected mothers.** Infants of HIV-infected mothers may be exposed to HIV in utero, at delivery or during breast-feeding. The neonatal immune response may have a role in determining vertical transmission. We will estimate the timing of HIV infection by DNA-PCR on blood spots from cord blood, and samples obtained at 6 weeks and 18 months after delivery. We will examine the effect of maternal helminth infections, and their treatment, on immune responses in cord blood and in infants at one year of age, by including HIV p24 antigen in the whole blood assay procedure. More detailed studies will be done on selected participants, using ELIspots or intracellular cytokine staining to identify responses by cell type and cytokine production. Cells will be stimulated with whole viral lysate, or with vaccinia constructs containing HIV genes to ensure class I presentation for CD8+ T cell responses. Potential confounding factors to be considered in these studies include possible associations between maternal helminth infection, or treatment of helminths, and maternal CD4+ T-cell count and viral load (Appendix 1), and the mother's choice of breast feeding practices. The numbers of subjects in the categories of maternal helminth infection and treatment will be small (Appendix 2 B), but will be sufficient to detect effects of a similar magnitude to those in our preliminary studies.

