#### **CHILDREN**

At One Year Follow-Up Children will be randomised to receive routine albendazole every 3 months or placebo, starting at 15 months. All will receive annual selective treatment based on stool examination.						
Group C1	Group C2					
Albendazole every 3 months and annual	Placebo every 3 months and annual					
selective treatment.	selective treatment.					

Annual Follow-Up Visits to Age 5 Years	
Helminths present, treated	Helminths absent

The analysis for the effect of maternal intestinal nematode infection will compare groups according to the presence or absence of intestinal nematodes at the antenatal visit, and whether or not they were treated; i.e. outcomes will be compared for children of mothers in groups G1-2-5-6 (intestinal nematodes, treated), G3-4-7-8 (intestinal nematodes, not treated), G9-10-13-14 (no intestinal nematodes, treated) G11-12-15-16 (no intestinal nematodes, not treated). The findings will be adjusted for the presence or absence of schistosomiasis, treatment with praziquantel, and the presence or absence of helminths at delivery. The overall effect of albendazole treatment during pregnancy will be determined by comparing G1-2-5-6-9-10-13-14 vs G3-4-7-8-11-12-15-16.

[figure not shown]
The analysis for the effect of maternal schistosomiasis will compare groups according to the presence or absence of schistosomiasis at the antenatal visit, and whether or not they were treated; i.e. outcomes will be compared for children of mothers in groups G1-3-9-11 (schistosomiasis, treated), G2-4-10-12 (schistosomiasis, not treated), G5-7-13-15 (no schistosomiasis, treated) G6-8-14-16 (no schistosomiasis, not treated). The findings will be adjusted for the presence or absence of intestinal nematodes, treatment with albendazole, and the presence or absence of helminths at delivery. The overall effect of praziquantel treatment during pregnancy will be determined by comparing G1-3-5-7-9-11-13-15 vs G2-4-6-8-10-12-14-16.

The analysis for the effect of intestinal nematodes in children will compare groups according to whether they receive routine albendazole every 3 months or annual selective treatment; i.e. outcomes for children in groups C1 and C2 will be compared. The presence or absence of helminths at annual follow up visits will be taken into account.

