#### Confounders / explanatory variables in addition to those considered above:

# Helminth risks sanitation

water source wearing of shoes

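### Appendix 4 adjusts the maternal infected-versus-uninfected comparisons for worm and study-drug terms only, leaving them open to confounding by variables the protocol lists elsewhere

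*Protocol*

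**What the plan says.** Aims 1 and 2 each contain two questions: the effect of maternal infection and the effect of treating it. Only treatment is randomised. The text on Aims 1 and 2 under Interventions and exposures says the nematode effect will be found by comparing children of mothers with and without nematodes in pregnancy, and points to Appendix 4.

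Appendix 4 (Plan for Analysis) then names the covariates:

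- Maternal nematodes: "The findings will be adjusted for the presence or absence of schistosomiasis, treatment with praziquantel, and the presence or absence of helminths at delivery".
- Maternal schistosomiasis: "The findings will be adjusted for the presence or absence of intestinal nematodes, treatment with albendazole, and the presence or absence of helminths at delivery".

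Confounding is handled in three other places, each with a different scope:

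- Aim 4 (childhood schistosomiasis) states that "important potential nutritional and environmental confounding factors for the effects of helminths are known to exist" and continues: "These will be recorded and appropriate adjustments will be made".
- Outcome (2), the HIV-response outcome, says: "Potential confounding factors to be considered in these studies include possible associations between maternal helminth infection, or treatment of helminths, and maternal CD4+ T-cell count". It goes on to viral load and the mother's feeding choice.
- Appendix 7 lists education, literacy, occupation, housing, possessions, tribe, gravidity, maternal HIV, sanitation, water source, shoe wearing and malaria. These stand under birth and maternal outcomes.

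**The concern.** Hypotheses 1 and 2 concern infection itself, so part of the answer rests on the infected-versus-uninfected contrasts. Poor housing and sanitation can plausibly raise both a mother's chance of carrying worms and her child's chance of diarrhoea, pneumonia or malaria. An analysis adjusted only for the other worm group, the other drug and helminths at delivery would read any such shared cause as an effect of maternal helminths.

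The protocol accepts this problem for Aim 4, where exposure is observational. Maternal infection is observational in the same sense, yet its stated covariate list has no such term. The results will be used: Appendix 9, main study (b), plans an analysis of maternal helminths against infant disease and immune responses. It is meant to inform safety and ethical questions and the review of sample size, and the same appendix says such results may be publishable.

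**Working it through.** **1. Text comparison.** No figure in the protocol depends on this covariate list, so there is none to reproduce. The question is whether the listed confounders reach the child outcomes.

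| Place | Confounders named | Applies to |
|---|---|---|
| Appendix 4 | other worm group, other drug, helminths at delivery | maternal-infection comparisons in children |
| Aim 4 | nutritional and environmental, not itemised | childhood schistosomiasis |
| Outcome (2) | maternal CD4+ count, viral load, feeding choice | HIV responses |
| Appendix 7 | socioeconomic, gravidity, HIV, sanitation, water, shoes, malaria | birth and maternal outcomes |

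Nothing extends the last three rows to Outcome (1), vaccine responses, or Outcome (3), disease incidence, in the maternal-infection comparisons.

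**2. Illustration for disease incidence.** Suppose maternal infection truly has no effect.

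Inputs from the protocol:
- 23% nematode prevalence (Appendix 2B, a minimum estimate);
- 2 × 1170 = 2340 children, and 3 years' median follow-up from the tuberculosis calculation (Sample size estimates);
- malaria about 100, and ALRI above 10, per 100 person-years (same section).

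Assumed, because the protocol gives no values:
- one household factor present in 60% of infected and 40% of uninfected mothers;
- confounder rate ratio g of 1.5 or 2;
- episode counts varying 3 or 5 times Poisson.

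Spurious rate ratio = [1 + 0.6(g − 1)] / [1 + 0.4(g − 1)]:
- g = 1.5: 1.30 / 1.20 = 1.083, log 0.0800;
- g = 2: 1.60 / 1.40 = 1.143, log 0.1335.

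Expected malaria episodes over three years are 0.23 × 2340 × 3 = 1615 and 0.77 × 2340 × 3 = 5405. The Poisson SE of the log rate ratio is √(1/1615 + 1/5405) = 0.0284. Multiplied by √3 it is 0.0491, and by √5 it is 0.0634. At 3 times Poisson, z = 0.0800/0.0491 = 1.63 or 0.1335/0.0491 = 2.72.

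The same steps with fewer events give the chance of P < 0.05 under no true effect (g = 1.5 to g = 2; nominal 5%):

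| Outcome and follow-up | 3 × Poisson | 5 × Poisson |
|---|---|---|
| Malaria, 3 years | 37–78% | 24–56% |
| Malaria, 1 year | 16–35% | 11–23% |
| ALRI, 3 years | 8–14% | 7–10% |
| ALRI, 1 year | 6–8% | 6–7% |

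The ALRI rows depend on the assumed over-dispersion. With none, the three-year SE is √(1/161.5 + 1/540.5) = 0.0897, so z = 0.89 or 1.49 and the chance is about 15–32%.

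**3. Other assumed strengths.** With 30% prevalence of the factor in uninfected mothers:
- 40% in infected, g = 1.5: 1.20 / 1.15 = 1.04;
- 50% in infected, g = 2: 1.50 / 1.30 = 1.15;
- 60% in infected, g = 3: 2.20 / 1.60 = 1.38.

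**4. Vaccine responses.** The protocol gives nothing from which to compute a bias. Appendix 1 does show that the issue can arise. In HIV-positive adults before treatment, 51% of those with helminths and 31% of those without had an IFN-γ response to the *M. tuberculosis* antigen (P = 0.05). The protocol says the difference was explained by adjusting for CD4+ count. A non-helminth covariate therefore changed how an infected-versus-uninfected immune comparison should be read.

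**The case against.** Appendix 4 does not call its list exhaustive. It is largely a map of which of the sixteen groups are compared, and a full covariate list is commonly left to a statistical analysis plan, which may exist and is not shown. Outcome (2) names confounders that Appendix 4 omits, so the authors did not treat that list as complete. Appendix 6 leaves later analyses to be planned from earlier ones. On this view all that is missing is a cross-reference.

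Much of this stands. A reader might infer that the protocol forbids further adjustment, or that the contrasts will certainly be confounded. The text supports neither: the list is open, and the size of any bias rests on strengths the protocol does not supply. A reader might also take 37–78% as the expected false-positive rate. That range belongs to one of the commonest outcomes, over three years, under assumed imbalances; the other rows of the table are much lower.

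Nor does the point reach the trial's main comparisons. Overall albendazole, overall praziquantel and C1 versus C2 are randomised, and the cohort size was proposed for the albendazole contrasts in pregnancy and childhood. Treated versus untreated within an infection stratum is also randomised. These baseline variables do not confound any of them.

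What survives is that the protocol did choose and write down a covariate set for a non-randomised contrast. That set leaves out the kinds of factor the protocol elsewhere treats as confounders. This goes beyond detail deferred to a later document.

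**Conclusion.** The point holds for the infected-versus-uninfected maternal comparisons of Outcomes (1) and (3). Followed as written, Appendix 4 leaves them open to confounding by socioeconomic, sanitation and HIV-related factors. Outcome (2) has partial cover from its own text.

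The size is unknown. Under the assumed 60% versus 40% exposure and 1.5- to 2-fold risk, the spurious rate ratio is about 1.08 to 1.14. That materially inflates false positives for common outcomes such as malaria. For ALRI the inflation is small if counts vary three times Poisson or more (6–14%). No size can be given for vaccine responses. The randomised contrasts and Hypothesis 3's treatment comparisons stand. This is an inconsistency in the stated analysis that is cheap to repair and does not call the design into question.

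**What to change.** In Appendix 4, state that infected-versus-uninfected comparisons of child outcomes are also adjusted for these baseline variables:

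- from Appendix 7: education, occupation, housing and possessions, sanitation, water source, shoe wearing, gravidity and maternal HIV;
- area of residence;
- for the HIV-response outcome, the factors named under Outcome (2).

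Use maternal malaria at enrolment only in a sensitivity adjustment. The Background and Aim 3 both discuss helminths altering malaria, so it may be a consequence of infection, and adjusting for it could remove part of the effect under study. Report the randomised contrasts separately from the observational ones.

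The cost is about a paragraph of text, slightly more analysis, and some loss of records with missing covariates. The enrolment visit already collects demographic and socioeconomic details and HIV serology. Sanitation, water source and shoe wearing are listed in Appendix 7 but not itemised in the enrolment visit, so check that the enrolment form records them.

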#### **Specific Aim:**

To examine the impact of helminths on the response to immunisation, and on susceptibility to infectious diseases in childhood, in a cohort of 2500 mothers and their children in Entebbe, Uganda. The study will have three randomised, placebo-controlled comparisons as well as observational components.

1. To examine the effects of maternal infection with intestinal nematodes, and of the treatment of maternal nematode infection in pregnancy. Mothers will be randomised to receive treatment with albendazole or placebo during the second to third trimester of pregnancy.

Mothers who are severely anaemic (haemoglobin  $\leq 8g/dl$ ) will be excluded from randomisation and treated with albendazole.

2. To examine the effects of maternal schistosomiasis, and of the treatment of schistosomiasis in pregnancy. Mothers will be independently randomised to receive treatment with praziquantel or placebo during the second to third trimester of pregnancy.

Mothers who have persistent diarrhoea with blood in the stools will be excluded from randomisation, investigated, and treated for schistosomiasis if present.

Thus the study will comprise four groups of mothers, according to treatment during pregnancy: (1) treated with both albendazole and praziquantel; (2) treated with only albendazole; (3) treated with only praziquantel; (4) no anti-helminthic treatment.

All mothers will have a second stool sample taken at delivery. All mothers will be mass treated with albendazole and praziquantel after delivery.

- **3.** To examine the effects of acquisition of intestinal nematodes during childhood and of regular mass treatment in childhood. After one year of age, children will be randomised to receive albendazole or placebo every 3 months. All children will receive annual, selective treatment based on stool analysis.
- **4.** To examine the effects of childhood schistosomiasis. This component will be observational. Children will receive annual, selective treatment based on stool analysis.

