Mothers: six weeks after enrolment. Protocol amendment, March 2003. "Effect of praziquantel treatment during pregnancy on anti-schistosome immune responses in pregnant women and their infants." All mothers will be requested to provide a second stool sample and a second blood sample (maximum 30 ml) to allow evaluation of the effects of treatment during pregnancy at a

consistent interval after treatment. This is particularly pertinent to the study of the effects of treating schistosomiasis.

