infections in utero may modulate the development of immune response to helminths in the offspring and thereby influence susceptibility to both infection and disease induced by the same species. Such effects may be altered by treatment during pregnancy. We will therefore investigate in particular detail the effects of exposure to schistosomiasis, and to praziquantel treatment in utero, on the prevalence of schistosomiasis in children at age five years, and on the regulatory immune response in these children. Furthermore, these effects could "spill over" to influence the development of responses to other antigens such as allergens. This amendment has been developed to examine these possibilities by

1) Determining the prevalence and intensity of S. mansoni among the children at 5 years and effect of the treatment during pregnancy on these parameters.

Treatment of maternal schistosomiasis during pregnancy could affect the development of responses to schistosomiasis, and hence susceptibility to infection, in several ways. For example, increased *in-utero* sensitisation of the children might increase resistance to schistosomiasis infection and minimise disease morbidity. Reduced sensitisation or no sensitisation of the children might increase susceptibility of the children to infection and predispose to early and severe morbidity. Tolerance on the other hand, if it occurs, might be associated with increased susceptibility to infection as is the case in lymphatic filariasis. These possibilities will be examined by comparing the prevalence as well as intensity of *S. mansoni* infection between the children of women who were treated during pregnancy and those who were not, alongside children from uninfected women.

The collection of three stool samples at age five years in the nested cohort of *S. mansoni*-exposed children will allow us to fulfil this objective by improving on the sensitivity of parasitological stool analysis for the purpose of identifying any children infected with S. mansoni at 5 years.

2) Determining immune responses including regulatory T cell responses to schistosome antigens and allergen related antigens.

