- The delay in treating mothers randomised to treatment after delivery would be, at most, just over 7 months, since mothers would not be treated in the first trimester in any case. There appears to be no evidence that progression of disease caused by schistosomiasis is any faster in pregnant women than in other adults. Persistent diarrhoea with blood is considered to be the pathological effect of chronic schistosomiasis most likely to show an immediate response to treatment, so we have planned to exclude women with these symptoms from the study, investigate them, and treat them if schistosomiasis is found. Otherwise, chronic schistosomiasis, including hepatosplenic schistosomiasis, is frequently asymptomatic, or the symptoms are non-specific and often ignored. The severe sequelae of long-term, heavy infection, such as portal hypertension and oesophageal varices, are unlikely to be much affected by a delay in treatment of, at most, just over 6 months. Therefore, as far as we know, the delay in treatment in some mothers is unlikely to have serious adverse consequences for their health.
- The prevalence of schistosomiasis in the pilot study (>20%) would justify a mass treatment approach if treatment in pregnancy were found to be specifically beneficial to the mother or child. In addition, examination of the single stool sample obtained may detect only about 60% of infected mothers. Therefore we have proposed to study a mass treatment intervention in pregnancy rather than to use selective treatment.

Advice has been given by colleagues at the Ministry of Health, and Uganda Virus Research Institute (UVRI).

Protocol amendment, January 2009. The following additional ethical considerations relate to the introduction T-spot.TB® testing for TB infection among five and six year olds, and to the use of stored samples for investigation of herpesviruse infections.

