#### **B.** Estimates of helminth infection in mothers.

During enrolment for the study described in Appendix 1, a sample of individuals attending the voluntary HIV testing centre at UVRI, who were found to be HIV-negative, were asked to bring stool samples to identify HIV-negative controls with schistosomiasis. Stools were examined by the Kato-Katz method only, so the results for nematodes are underestimates, and *Strongyloides* was not sought. From the results for these subjects, the minimum prevalence of helminth infections for adult women in Entebbe is expected to be as follows:

	S. mansoni	hookworm	Trichuris	Ascaris	all nematodes	all worms
prevalence	12%	18%	5%	3%	23%	32%

In a cohort of 2500 women, the minimum expected, numbers by HIV status would be:

	S. mansoni	hookworm	Trichuris	Ascaris	all nematodes	all worms
HIV- (2250)	270	405	112	68	518	720
HIV+ (250)	30	45	12	8	58	80

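### Appendix 4 fixes maternal schistosomiasis status at the antenatal visit, uses neither later stool to classify untreated mothers, and adjusts for one of them

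*Protocol*

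**What the plan says.** Appendix 4 of the protocol forms groups G1 to G16 from antenatal infection status and randomised treatment. For schistosomiasis, outcomes in the children are compared "according to the presence or absence of schistosomiasis at the antenatal visit, and whether or not they were treated". The result is adjusted for nematodes, for albendazole, and for whether helminths are present at delivery. The nematode analysis has the same structure.

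The Ethical Considerations section, arguing for mass rather than selective treatment, says that "examination of the single stool sample obtained may detect only about 60% of infected mothers".

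Two later stools are planned. The Specific Aim says "All mothers will have a second stool sample taken at delivery", and the March 2003 amendment adds, six weeks after enrolment, "All mothers will be requested to provide a second stool sample and a second blood sample". The six-week stool does not appear in Appendix 4. The delivery stool appears there only as an adjustment variable.

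For five-year-olds exposed in utero, the January 2009 amendment takes three stools, with the aim of "improving on the sensitivity of parasitological stool analysis". The Parasitology section adds serum CAA for HIV-infected women.

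**The concern.** Hypothesis 1 and Aims 1 and 2 ask what untreated maternal infection does to the child. If the test misses about two infected mothers in five, those mothers enter the uninfected comparison group and pull the contrast towards no effect. The protocol acknowledges the low detection rate but does not carry it into the analysis.

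In mothers given placebo for the relevant drug, the later stools are not altered by that drug, so they are further readings of exposure during pregnancy. Appendix 4 does not use them for this. Adjusting for the delivery reading instead can remove part of the effect being estimated. At stake is bias towards no effect, and lost precision, in a contrast that tests a stated hypothesis.

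**Working it through.** **Inputs from the protocol**
- Single-stool sensitivity 0.6, for schistosomiasis (Ethical Considerations). It rests on cited sources and cannot be re-derived.
- Prevalence: "The prevalence of schistosomiasis in the pilot study (>20%) would justify a mass treatment approach"; and 12% for *S. mansoni* in Appendix 2B, where "the minimum prevalence of helminth infections for adult women in Entebbe is expected to be as follows".
- Cohort of 2500.

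**Assumptions**
- 12% and 20% are prevalences as detected by one stool.
- Specificity is 100%, and sensitivity is 0.6 at every stool.
- No infection is gained or lost between stools.
- Missed infections affect the child as much as detected ones.
- Half the cohort, 1250 mothers, receives praziquantel placebo.
- Between-stool correlation r within an infected woman is 0 to 0.5.

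**The plan's own figure.** Appendix 2B gives expected numbers: "In a cohort of 2500 women, the minimum expected, numbers by HIV status would be". For *S. mansoni*, 2250 × 0.12 = 270 and 250 × 0.12 = 30, total 300. This reproduces.

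**One stool.** True prevalence p = observed / 0.6, so 0.12 gives 0.20 and 0.20 gives 0.333. Infected share of the negatives = 0.4p / (1 − 0.6p).
- p = 0.20: 0.08 / 0.88 = 9.1%. Missed mothers: 250 − 150 = 100 of 1250.
- p = 0.333: 0.133 / 0.80 = 16.7%. Missed mothers: 417 − 250 = 167 of 1250.

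With no false positives, the retained fraction of the true difference is one minus that share: 0.91 and 0.83.

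**One stool, adjusted for the delivery stool.** In untreated mothers, take a linear model with both readings. By symmetry the coefficient on the enrolment stool is c / (v + w), where c = 0.6p(1 − p), v = 0.6p(1 − 0.6p), and w is the covariance of the two stools.
- Independent stools, w = 0.36p(1 − p): 0.59 (p = 0.20) and 0.56 (p = 0.333).
- r = 0.5, w = 0.48p − 0.36p²: 0.096 / (0.1056 + 0.0816) = 0.51 and 0.1333 / (0.16 + 0.12) = 0.48.

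Retention therefore falls from 0.83-0.91 to about 0.48-0.59 if the covariate is infection with the same species. Appendix 4 names helminths in general, which is a weaker proxy and would be expected to remove less. A model pooled with treated mothers would also give a different figure.

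**Any positive of three stools.**
- Independent stools: sensitivity = 1 − 0.4³ = 0.936.
- r = 0.5 (beta-binomial): probability of missing all three = (0.4 × 1.4 × 2.4) / (1 × 2 × 3) = 0.224, so sensitivity = 0.776.

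| | One stool | Three, r = 0.5 | Three, independent |
|---|---|---|---|
| Infected among negatives, p = 0.20 | 9.1% | 5.3% | 1.6% |
| Infected among negatives, p = 0.333 | 16.7% | 10.1% | 3.1% |
| Retained difference, p = 0.20 | 0.91 | 0.95 | 0.98 |
| Retained difference, p = 0.333 | 0.83 | 0.90 | 0.97 |
| Relative information, p = 0.20 | 1 | 1.35 | 1.69 |
| Relative information, p = 0.333 | 1 | 1.40 | 1.81 |

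Information is taken as (retained fraction)² × d(1 − d), with d the proportion called positive. For p = 0.333, one stool gives 0.833² × 0.20 × 0.80 = 0.111, and three independent stools give 0.969² × 0.312 × 0.688 = 0.202; ratio 1.81.

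**What shrinks the gain**
- Two stools instead of three, r = 0.5: information ratio 1.23 to 1.26.
- Specificity 99% per stool, p = 0.20, r = 0.5: retained difference falls from 0.85 to 0.81, although information still rises about 1.2-fold.
- Restricting to complete sets when 70% have them (assumed): 0.7 × 1.35 = 0.95 to 0.7 × 1.81 = 1.27, so the gain can vanish.

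**If the new definition were used only in untreated mothers within the four-group comparison.** With independent stools, the uninfected groups would hold 16.7% missed infections in the treated arm and 3.1% in the untreated arm (9.1% and 1.6% at p = 0.20). Even with no treatment effect, their contrast would be biased by 0.136 (0.075) of the infection effect.

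**The case against.** The strongest defence is that one pre-randomisation definition, applied identically in every arm, is sound. The Aims 1 and 2 text bases treatment effects in infected mothers on infection known before treatment, and the four groups already include infected-untreated and uninfected-untreated mothers. This stands for treatment comparisons, and it is why the new definition must stay out of them. It does not answer the misclassification in the contrast within untreated mothers.

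Other points also stand:
- The 60% is given for schistosomiasis only; the documents give no figure for nematodes.
- HIV-infected women, 250 of 2500 in Appendix 2B, also have serum CAA, although Appendix 4 does not say whether it enters the classification. A reader might infer that every mother's status rests on one stool; the documents do not support that.
- The later stools will be incomplete. The six-week stool came by amendment in March 2003, while Appendix 9 expects the first year of main-study enrolment to be complete around October 2003. The delivery stool is taken before the mother leaves hospital, so women delivering elsewhere may lack it.
- Later stools also detect infections acquired after enrolment.

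One could add that supplementary exposure definitions belong in a statistical analysis plan. Here, however, Appendix 4 itself fixes both the classification and the delivery adjustment.

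**Conclusion.** The point holds for the observational infected-versus-uninfected contrast among untreated mothers. For schistosomiasis, at 12-20% observed prevalence, the plan retains about 83-91% of the true difference, and less once delivery status is adjusted for. Using all available stools would raise sensitivity to about 0.78-0.94 and retention to 0.90-0.98, with roughly 1.35 to 1.8 times the information if all three are present. The pilot prevalence is stated as above 20%, so the upper end of the bias could be exceeded. If missed infections are lighter and matter less to the child, both the bias and the gain are smaller.

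A reader might infer that the trial's treatment results are compromised. They are not: the overall albendazole and praziquantel comparisons do not use infection status. A reader might also infer that the later stools offer a nearly complete remedy without cost. That would need near-independent stools, near-perfect specificity and few missing samples, none of which the documents establish. For nematodes only the direction of benefit is supported.

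**What to change.** Add to Appendix 4 an infected-versus-uninfected analysis within mothers given praziquantel placebo:
- Define infection as any positive stool at enrolment, six weeks or delivery, plus CAA where measured.
- Stratify by, or adjust for, the number of stools provided, rather than restricting to complete sets.
- Do not adjust for infection with the same species at delivery.

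Do the same for nematodes within mothers given albendazole placebo. Keep the enrolment-stool definition for every treated-versus-untreated comparison.

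The cost is a derived variable and an added analysis for each infection; no new samples or visits are needed. The downsides should be stated with the analysis: infections acquired after enrolment count as exposed, women with fewer stools remain less well classified, false positives accumulate over repeated stools, and the definition of infection differs from that in the treatment comparisons.
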